7 MEASUREMENTS OF TREATMENT COMPLIANCE

There are no assessments of compliance in this NIS.

8 EFFICACY ANALYSES

8.1 Statistical analysis of the primary efficacy variables

Summaries of the primary variables will be conducted in the FAS and the modified FAS. All efficacy data will be listed in the ES.

8.1.1 Derivations of primary efficacy variables

8.1.1.1 Seizure frequency response

A responder is defined as a patient who experiences a 50% or greater reduction in partial-onset seizure frequency from Visit 1 (Baseline) to Visit 3 (Month 6 or end of Observation Period).

8.1.1.2 Patient Global Impression of Change

Patients will be categorized based on their PGIC value collected at Visit 3 into the following groups:

- Improved: scores 1 to 3
- No change: score 4
- Worsened: score 5 to 7

8.1.2 Primary analysis of primary efficacy variables

8.1.2.1 Seizure frequency response

The number and percentage of responders, where a responder is a patient experiencing a 50% or greater reduction in partial onset seizure frequency from Visit 1 (Baseline) to Visit 3 (Month 6 or end of Observation Period), will be presented. The 95% CI for the percentage of responders will be calculated using the 2-sided Clopper-Pearson method.

Percentages are based on the number of patients with available data.

The seizure frequency response rate and corresponding 95% CI (2-sided Clopper-Pearson method) will be presented in each of the subgroups described in Section 4.8.

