11.3 Planned analyses

11.3.1 Analysis of the primary variable

The number and percentage of responders, where a responder is a patient experiencing a 50% or greater reduction in partial-onset seizure frequency from Visit 1 (Baseline) to Visit 3 (Month 6 or end of Observation Period), will be presented for the FAS.

The number and percentage of patients with each PGIC value will be summarized at Visit 3 (Month 6 or end of the Observation Period) for the FAS. The number and percentage of patients who improved (scores 1 to 3), had no change (score 4), and worsened (scores 5 to 7) will also be provided.

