2.4 Determination of sample size

A sample size of 100 enrolled patients to obtain 93 evaluable patients was chosen for this study based on an expected 6-month responder rate (where a responder is a patient experiencing a 50% or greater reduction in partial onset seizure frequency from Visit 1 [Baseline] to Visit 3 [Month 6 or end of Observation Period]) of 60% with an expected precision in the 95% confidence interval (CI) of approximately $\pm 10\%$ for this estimate of response.

When the sample size is 93, a 2-sided 95% CI for a single proportion using the large sample normal approximation will extend 0.10 from the observed proportion for an expected proportion of 0.60.

Recruitment will be stopped at 100 enrolled patients and withdrawals will not be replaced.

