3 DATA ANALYSIS CONSIDERATIONS

3.1 General presentation of summaries and analyses

All statistical analyses will be performed in an exploratory manner. Statistical analyses and generation of tables, figures, and listings will be performed using SAS version 9.1 or higher using validated program code according to relevant standard operating procedures. All tables and listings will use courier new font size 9.

A complete set of data listings containing both, documented data and all calculated data (eg, changes from Baseline) will be generated.

For continuous variables, summary statistics (number of available observations, mean, standard deviation (SD), minimum, lower quartile, median, upper quartile and maximum) will be tabulated. For categorical variables, frequency tables (number and percentages per category) will be presented. Unless otherwise specified the denominator for calculating percentages will be the number of patients in the respective population.

Unless otherwise noted, all percentages with the exception of 0 and 100 will be expressed to 1 decimal place, and 100% will be presented as integer. If a category has the frequency 0, the percentage value will be omitted. Mean and median changes from Baseline lower than the minimal displayable change will be displayed without sign (eg, -0.00 will be displayed as 0.00).

Decimal places for descriptive statistics will always apply the following rules:

- n will be an integer
- Mean, SD, and median will use 1 additional decimal place compared to the original data
- Minimum and maximum will have the same number of decimal places as the original value

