3.2.2 End date of the Observational Period

The end date of the Observational Period will be the date of Visit 3, which is approximately 6 months after Baseline for subjects completing the Treatment Period, or the Withdrawal Visit for subjects who discontinued during the Observational Period. If a subject does not have a Visit 3 for any reason including death, then either the date of early withdrawal or the date of last known dose of study drug during the Observational Period, whichever is later, will define the end date of the Observational Period.

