3.5.3 Full Analysis Set

The Full Analysis Set (FAS) is defined as all patients in the SS who have at least 1 post-Baseline PGIC or seizure assessment. The FAS will be used for the analysis of the primary and most secondary variables including any subgroup analyses. In addition, demographic and baseline summaries will be based on the FAS.

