4.2 Handling of dropouts or missing data

All available data will be used for analysis.

Missing data of the variables will not be substituted. However, imputations of missing values as described in this section will be done in order to use the available data as much as possible, eg, imputations for missing or partial values for dates will be applied to calculate derived variables or to determine prior and concomitant medication

With respect to ADRs, events with missing information about action taken regarding UCB suspected drug status are regarded as ADRs leading to premature discontinuation. Events with no

answer to the question “Seriousness indicators: Is the event/reaction serious?” will be regarded as serious.

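### Both primary percentages leave out FAS patients who have no usable Visit 3 value, which probably raises the responder rate by a few points

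*SAP*

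**What the plan says.** Protocol 11.3.1 says that the number and percentage of responders "will be presented for the FAS", and it names the same set for PGIC. It gives no rule for patients without a Visit 3 value.

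SAP 3.5.3 defines the FAS as "all patients in the SS who have at least 1 post-Baseline PGIC or seizure assessment". Protocol Table 15-1 schedules seizure documentation at Visits 2 and 3 but PGIC only at Visit 3. A Visit 2 seizure count alone therefore puts a patient in the FAS.

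SAP 3.1 sets a default: "Unless otherwise specified the denominator for calculating percentages will be the number of patients in the respective population". SAP 8.1.2.1 replaces that default for the responder rate with "Percentages are based on the number of patients with available data", and SAP 8.1.2.2 repeats the sentence for PGIC. Under SAP 4.2, "Missing data of the variables will not be substituted".

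Patients who stop early should have the Visit 3 assessments at a Withdrawal Visit (Protocol 5, SAP 2.3). SAP 3.2.2 foresees that some will have neither: its fallback rule for dating the end of observation begins "If a subject does not have a Visit 3 for any reason including death". SAP 3.9 lists no change to the protocol-defined analyses.

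**The concern.** The analysis set and the denominator are different groups. A patient who has a Visit 2 seizure count and no later usable value is a FAS member with neither primary outcome. Under the SAP that patient appears in neither primary percentage.

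Such losses are unlikely to be random. Protocol 8.2 withdraws patients whose Baseline AED dose must rise, who need more than two AEDs besides LCM, or whose physician stops LCM. Some of these patients will have no Withdrawal Visit assessment, and they are probably less often responders than those who stay. The responder rate would then describe patients still under assessment at the end, while the table heading names the FAS. The Clopper-Pearson interval reflects sampling error only and does not show this shift.

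**Working it through.** **The planned figure.** Inputs from Protocol 11.5 and SAP 2.4: expected rate 0.60, two-sided 95% CI, half-width 0.10, 93 evaluable of 100 enrolled.

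- n = 1.96² × 0.60 × 0.40 / 0.10² = 92.2, rounded up to 93.
- Half-width at n = 93: 1.96 × √(0.24/93) = 0.0996.
- 93/0.93 = 100, so the plan allows for a loss of 7.

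The stated sample size reproduces.

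**Effect of the denominator.** Let m be the share of the FAS without a usable Visit 3 seizure value and r the responder rate among those who have one. The SAP reports r. Over the whole FAS, with missing counted as non-response, the rate is r(1 − m), so the gap is r × m.

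The documents give no value for m, so the shares below are assumptions. They use a FAS of 100 and r of about 0.60. Clopper-Pearson 95% CIs are in brackets.

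| m | Available data | Over the FAS | Gap (points) |
|---|---|---|---|
| 5% | 57/95 = 60.0% (49.4 to 69.9) | 57/100 = 57.0% (46.7 to 66.9) | 3.0 |
| 7% | 56/93 = 60.2% (49.5 to 70.2) | 56/100 = 56.0% (45.7 to 65.9) | 4.2 |
| 10% | 54/90 = 60.0% (49.1 to 70.2) | 54/100 = 54.0% (43.7 to 64.0) | 6.0 |
| 20% | 48/80 = 60.0% (48.4 to 70.8) | 48/100 = 48.0% (37.9 to 58.2) | 12.0 |

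The 7% row is the plan's own loss on the assumption that all 7 patients are in the FAS. If the 7 were outside it, they would add nothing to the gap.

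The size of the FAS matters little. With a FAS of 93 and 5 missing, 53/88 = 60.2% becomes 53/93 = 57.0%, a gap of 3.2 points.

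The gap reaches 10 points when m = 0.10/0.60 = 16.7%.

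**What the gap measures.** If the missing patients responded at rate q, the full-FAS rate would be r(1 − m) + q × m, and the available-data rate would be too high by m(r − q). The table shows the limiting case q = 0. In the 7% row the possible range runs from 56/100 = 56.0% (none responded) to 63/100 = 63.0% (all responded). The available-data rate is too high whenever q is below r.

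**The case against.** The case for leaving the SAP as it is has several parts.

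- **Protocol conflict.** A reader might infer that the SAP contradicts the protocol. Protocol 11.3.1 names an analysis set but no missing-data rule, Protocol 11 leaves detail to the SAP, and SAP 8.1 also uses the FAS. The SAP 3.1 default allows exceptions, and 8.1.2.1 makes one openly. This stands: the denominator is an unexplained narrowing, not a proven breach.
- **Who is lost.** A reader might infer that everyone who withdraws, dies or is lost leaves the denominator. Patients with a usable Withdrawal Visit value are meant to stay in. Patients with no assessment after Baseline are outside the FAS under the protocol's own definition, so the SAP sentence does not remove them. This stands and narrows the group. SAP 3.2.1 places visits up to day 135 in the Visit 2 window while labelling Visit 3 as including Withdrawal Visits. Those statements need reconciling, but the present gap would remain afterwards.
- **Retention.** It is tempting to say that the same patients count as failures there. Early withdrawals do (SAP 3.10.7), but a completer whose Visit 3 value is missing is censored.
- **Sample size.** The planned CI rests on 93 evaluable patients, not on everyone enrolled with losses as failures. Evaluable is undefined, so this suggests an available-data denominator without settling it. Withdrawals are not replaced, but the plan already allows for 7 losses.
- **Other outputs.** Disposition, retention and discontinuation rates show the losses. They do not show how many FAS patients are absent from the primary percentage.
- **Last visit.** Protocol 11.2 has early withdrawals analyzed as far as their last attended visit. That could suggest using Visit 2, but no SAP rule carries Visit 2 data to Visit 3.
- **Descriptive study.** There is no test to distort. The effect is on the estimate, its CI and its label.

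**Conclusion.** The point holds for a limited group: FAS patients with an earlier assessment after Baseline and no usable Visit 3 or Withdrawal Visit value. They drop out of both primary percentages, and nothing replaces their data. For the responder rate the likely direction is upward. That is a judgement from the withdrawal rules, and it assumes that these patients respond less often than those observed.

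The size is unknown. The plan's own 100 and 93 give about 4 points if all 7 losses are in the FAS. A reader might infer an overstatement of 12 points or more, beyond the planned precision. That needs about a fifth of the FAS to lack Visit 3 data with none of them responding, and the documents support neither. Counting every missing patient as a non-responder gives a lower bound, not the true rate.

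**What to change.** 1. In SAP 8.1.2.1, present the responder rate with its Clopper-Pearson CI over the FAS, counting FAS patients without Visit 3 seizure data as non-responders. Show the available-data rate and CI next to it.
2. In SAP 8.1.2.2, use the FAS as denominator and add a missing row split by termination reason, with a line for completers whose PGIC is missing.
3. Report the number of FAS patients without Visit 3 data, separately for seizures and PGIC.
4. State the denominator choice in SAP 3.9.

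The cost is SAP wording and an extra column and row. Seizure counts, PGIC and termination reasons are already planned for collection. The drawback is a lower headline rate, which is conservative if some of the missing patients had responded. Showing both rates lets the reader see the difference.

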8.1.2.2 Patient's Global Impression of Change

The number and percentage of patients within each response category for PGIC (1=very much improved, 2=much improved, 3=minimally improved, 4=no change, 5=minimally worse, 6=much worse, and 7=very much worse) will be summarized.

Additionally, the number and percentage of patients who improved (impression of change <4), had no change (impression of change =4), and worsened (impression of change >4) will also be provided.

Percentages are based on the number of patients with available data.

Summaries of PGIC will be presented in each of the subgroups described in Section 4.8.

8.2 Statistical analysis of the secondary efficacy variables

Summaries of the secondary variables will be conducted in the FAS and modified FAS unless otherwise stated.

8.2.1 Retention rate

Retention rate is defined as the percentage of patients remaining in the study and on LCM treatment for 6 months (6-month retention rate). The number of patients remaining in the study and on LCM treatment for 6-months will be summarized with the retention rate in the SS, the FAS and the modified FAS. The retention rate will be derived using Kaplan-Meier methodology where patients who remain on treatment at the end of the 6-month Observation Period are censored at the date of last administration of LCM. A 2-sided 95% CI (based on Greenwood's formula) for the 6-month retention rate will be presented.

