11.1 Definition of analysis sets

For this NIS, the following definitions will apply:

The Enrolled Set (ES) is defined as all patients included in the study and for whom at least Visit 1 is documented. The ES will be used for patient disposition and patient data listings only.

The Safety Set (SS) is defined as all patients included in this study receiving treatment with LCM at least once in the study. The SS will be used for the analysis of the retention and discontinuation rates, time to discontinuation, safety data, and Baseline characteristics of the patients.

The Full Analysis Set (FAS) is defined as all patients in the SS who have at least 1 post-Baseline PGIC or seizure assessment. The FAS will be used for the analysis of the primary and most secondary variables.

The modified FAS is defined as all patients in the FAS ≥ 16 years of age and treated with daily LCM doses $\leq 400\text{mg}$, representing the on-label use of LCM.

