3.9 Changes to protocol-defined analyses

Not applicable.

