3.10.6 Retention rate

The 6-month retention rate is the percentage of patients remaining in the study and on LCM treatment for 6 months. This will be estimated using Kaplan-Meier methodology applied to the time to discontinuation of LCM. A cut of 180 days will be used for 6 months. The derivation of the time to discontinuation and the corresponding censoring flag are described in Section 3.10.7.

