3.10.7 Time to discontinuation of LCM

Time to discontinuation of LCM will be defined as

The date of last administration of LCM while in the study - the date of first dose of LCM + 1

If the date of last administration of LCM while in the study is not available the study termination date will be used. If the start date of LCM is missing, then it is assumed that the patient did not receive treatment and they would be consequently excluded from the relevant analysis sets and therefore from this analysis.

A censor flag will be derived where patients who completed the study are censored and patients who have discontinued LCM prior to the end of the 6-month Observation Period (early withdrawals) are not censored.

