8.2.2 Time to discontinuation of LCM

Time to discontinuation of LCM from the date of first dose of LCM will be analyzed using Kaplan-Meier methods for the SS, the FAS and the modified FAS. The median time to discontinuation (days) of LCM including corresponding 2-sided 95% CIs for the median time to discontinuation will be calculated. Patients who complete the 6-month Observation Period will be censored on the date of the final LCM administration or the study termination date if the date of the final LCM administration is not available.

Supportive Kaplan-Meier plots of time to discontinuation of LCM from the date of first dose of LCM will be presented for the SS, the FAS and the modified FAS.

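### Retention and time to discontinuation are also reported in the FAS and modified FAS, which leave out patients who stop LCM early and are never assessed again, so FAS retention is likely to be too high.

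*SAP*

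**What the plan says.** Protocol 11.1 assigns these variables to one set: "The SS will be used for the analysis of the retention and discontinuation rates, time to discontinuation". SAP 3.5.2 repeats this. The SAP's analysis sections then add two sets. In 8.2.1 the number retained "will be summarized with the retention rate in the SS, the FAS and the modified FAS". In 8.2.2 time to discontinuation "will be analyzed using Kaplan-Meier methods for the SS, the FAS and the modified FAS", with plots in all three sets.

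SAP 3.5.3 defines the FAS as "all patients in the SS who have at least 1 post-Baseline PGIC or seizure assessment". SAP 3.5.4 builds the modified FAS from the FAS by dropping anyone who ever receives more than 400 mg of LCM, and it repeats all efficacy analyses other than subgroup analyses in that set.

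Time runs from the first LCM dose (SAP 3.10.7). Completers are censored, and "patients who have discontinued LCM prior to the end of the 6-month Observation Period (early withdrawals) are not censored". For the retention rate, "A cut of 180 days will be used for 6 months" (SAP 3.10.6).

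Protocol 5 and SAP 2.3 ask early discontinuers to have the Visit 3 assessments as a Withdrawal Visit. SAP 3.2.2 nevertheless provides for patients who have no Visit 3.

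**The concern.** The clock starts at first dose, but FAS membership is settled later, by whether a PGIC or seizure assessment is ever recorded. That requirement suits response and PGIC, which cannot be computed without such a value. It does not suit a time-to-event variable that is fully observed without one. A patient who stops LCM in week 3, skips the Withdrawal Visit and does not come back has a known event time in the SS and does not exist in the FAS. Stopping early makes a missing assessment more likely, so membership is linked to the outcome.

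At stake is which retention figure gets quoted. SAP 8.2 makes the FAS and modified FAS the usual sets for secondary variables, and neither 8.2.1 nor 8.2.2 says how the FAS versions should be read beside the SS one. The only on-label retention figure comes from the modified FAS, which carries the same restriction.

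**Working it through.** **1. The plan's own figure.** Protocol 11.5 and SAP 2.4 give 93 evaluable patients for an expected responder rate of 0.60 and a 95% CI half-width of 0.10.

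- n = 1.96² × 0.60 × 0.40 / 0.10² = 92.2, rounded up to 93.
- Half-width at n = 93: 1.96 × √(0.24/93) = 0.0996.
- 93 / (1 − 0.07) = 100 enrolled.

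The figure reproduces. It concerns the responder rate. The documents state no expected retention rate and no expected SS-to-FAS gap.

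**2. How the two sets treat the same patient.**

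| Patient | SS | FAS |
|---|---|---|
| Stops early, has a Withdrawal Visit with PGIC or seizure data | event | event |
| Stops early, no assessment after Baseline | event | absent |
| Completes, has Visit 3 data | censored | censored |

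The sets differ in the second row, apart from any completer who has neither PGIC nor seizure data.

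**3. Size, by assumption.** Let the SS have 100 patients, let r be SS retention at day 180, and let k be the number of SS patients in the second row, all stopping before day 180. With nobody censored before day 180, FAS retention = 100r / (100 − k). For r = 70%: 70/99 = 70.7%, 70/97 = 72.2%, 70/93 = 75.3%.

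| SS retention | k=0 | k=1 | k=3 | k=5 | k=7 |
|---|---|---|---|---|---|
| 60% | 60.0% | 60.6% | 61.9% | 63.2% | 64.5% |
| 70% | 70.0% | 70.7% | 72.2% | 73.7% | 75.3% |
| 80% | 80.0% | 80.8% | 82.5% | 84.2% | 86.0% |

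The excess runs from zero at k=0, through 1.9 to 2.5 points at k=3, to 4.5 to 6.0 points at k=7.

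**4. Check with censoring.** A simulated Kaplan-Meier estimate at day 180 used discontinuations spread over days 7 to 169, completers censored over days 150 to 210, and removed patients drawn from those stopping by day 90. With 70 of 100 completing, mean retention went from 0.693 (SS) to 0.714 (FAS, 3 removed) and from 0.693 to 0.745 (7 removed). With 7 removed it went from 0.591 to 0.635 when 60 complete, and from 0.795 to 0.855 when 80 complete. The closed formula is therefore a fair guide. The upward direction is built in here, because only discontinuers are removed.

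**5. What would reverse the direction.** At 70% SS retention with 7 patients removed, FAS retention falls below the SS value only if at least 5 of the 7 are completers: (70 − 5)/93 = 69.9%, against (70 − 4)/93 = 71.0% with 4. This is unlikely, since completers have Visit 3.

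**The case against.** The SS estimate is still produced, is listed first, and is the one that Protocol 11.1 and SAP 3.5.2 name. Retention is a secondary variable in a descriptive study, and no decision rests on the FAS table. This stands, and it limits the point to the added tables and plots.

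Several stronger readings are tempting, but the documents do not support them:

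- **An undeclared departure from the protocol.** SAP 3.9 says "Not applicable" under changes to protocol-defined analyses. But Protocol 11.3.2 leaves the analysis set for each secondary variable to the SAP, and the SAP keeps the SS.
- **Immortal time.** FAS members are not guaranteed event-free until assessed. Someone who stops in week 3 and has a Withdrawal Visit in week 4 enters the FAS with a week-3 event. The problem is selection on having been assessed at all.
- **Both added sets biased upwards.** Patients who go above 400 mg may have stayed on LCM longer, and removing them could lower retention. The net direction in the modified FAS is unknown.
- **A distorted median.** At 60% to 80% retention neither set reaches its median by day 180. A change of status needs something like 47% in the SS, giving 47/93 = 50.5% in the FAS.
- **An established inflation of 2 to 6 points.** Both k and r are assumed, and k may be 0 or 1. The gap of 7 between enrolled and evaluable patients is nowhere said to be the SS-to-FAS gap. For scale, the 95% CI half-width at 70% with 100 patients is 1.96 × √(0.21/100), about 9 points, which exceeds every shift shown.

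It can also be said that deleting the FAS versions removes retention in the population used for the primary response. That is fair, and labelling them would meet it.

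**Conclusion.** The point holds for the supplementary estimates. Under the stated rules, an SS patient who stops LCM early and has no assessment after Baseline is a retention failure in the SS and is missing from the FAS. FAS retention is therefore likely to be too high, and its Kaplan-Meier curve too favourable. The modified FAS shares the restriction without a certain net direction. The SS result is not affected.

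The size cannot be derived from the documents. With an SS of 100, 70% SS retention and every excluded patient stopping before day 180, the excess is 0 points at k=0, 0.7 at k=1, 2.2 at k=3 and 5.3 at k=7, the last only if the 100-to-93 gap is the SS-to-FAS gap. It is worth correcting because the correction is cheap and the on-label retention figure has no version free of the restriction.

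**What to change.** - In SAP 8.2.1 and 8.2.2, make the SS the set for retention, time to discontinuation and the Kaplan-Meier plots.
- Take any on-label retention figure from SS patients who meet the SAP's own definition (daily dose of 400 mg or less), without requiring a post-Baseline assessment, and add a matching exception to SAP 3.5.4. The dose restriction is still a selection made after Baseline, so that figure needs a note saying so.
- If FAS or modified FAS versions are kept, label them supplementary and conditional on a post-Baseline assessment. Report how many SS patients are excluded and when they discontinued.
- Apply the same to the discontinuation rates in SAP 8.2.7 to 8.2.9. There the FAS restriction would lower the rates if the missing patients stopped for those reasons.

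The cost is SAP wording, and fewer tables if the FAS versions go. No new data are needed. The downside is a slightly less favourable retention figure.
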